**Table 1: Study Treatment Groups**

Subjects (n)	Treatment Group	Drug
12	A	Interferon beta-1a (Avonex®) low (7.5 µg)
12	B	Interferon beta-1a (Avonex®) intermediate (15 µg)
12	C	Interferon beta-1a (Avonex®) high (30 µg)
12	D	Peginterferon beta-1a (Plegridy®) low (31.25 µg)
12	E	Peginterferon beta-1a (Plegridy®) intermediate (62.5 µg)
12	F	Peginterferon beta-1a (Plegridy®) high (125 µg)
12	G	Placebo

### 3.2. Sample size

Up to 98 healthy subjects will be enrolled (84 subjects planned for treatment and up to 14 potential replacement subjects). Subjects will be randomized to one of 6 different active treatment arms (i.e. 12 per treatment arm) or placebo. This study did not have any formal sample size or power calculations. Doses expected to characterize the dynamic range of the primary PD biomarker (neopterin) were selected. A total of 12 subjects are planned per dose, which is slightly higher than a typical sample size for estimating values and variability of PK and PD measures in single ascending dose trials.

## 4. Study Endpoints

### 4.1. Primary Endpoints

- Neopterin area under the effect curve from time zero to last on-study timepoint (AUEC0-tb referred to as AUEC for brevity).
- Maximum increase from baseline in neopterin ( $\Delta$ Neopterindec, max)

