## Table of Abbreviation

Abbreviation	Definition
AUC 0-inf	area under the concentration-time curve from time zero to infinity
AUC 0-t	area under the concentration-time curve from time zero to last on-study sample
AUEC 0-t	area under the effect curve from time zero to last on-study sample
AUEC	area under the effect curve
pAUEC 0-t	percentage area under the effect curve from time zero to last on-study sample
CL/F	apparent clearance
C max	maximum observed concentration
EC 50	the exposure that gives-half maximal response, model parameter
ED 50	the dose that gives-half maximal response, model parameter
E max,exp	maximum PD response, model parameter – concentration analysis
E max,dose	maximum PD response, model parameter – dose analysis
FDA	Food and Drug Administration
IFN β-1a	interferon beta-1a (Avonex®)
K el	elimination rate
mg	milligram
ΔMxA dec, max	maximum increase from baseline in MxA protein
ΔNeopterin dec, max	maximum increase from baseline in neopterin
PD	pharmacodynamic
pegIFN β-1a	pegylated interferon beta-1a (Plegridy®)
PK	pharmacokinetic
RNA	ribonucleic acid
SC	subcutaneously
SD	standard deviation
T max	time of maximum concentration (C max )
t 1/2	terminal half-life
V/F	apparent volume of distribution

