## **3. Study Overview**

### **3.1. Study Design**

This is a randomized, double-blind, placebo-controlled, single-dose, parallel arm, pilot study. Healthy subjects will be randomized to one of three dose groups (low, intermediate, and high) for each drug (IFN  $\beta$ -1a and pegIFN  $\beta$ -1a) or placebo (See Table 1). The study will be conducted at one center in the United States (Spaulding Clinical Research unit in West Bend, Wisconsin).

Subjects randomized to Treatment Groups A, B, and C will stay in-house for the duration of the study and will be discharged on Day 7. Subjects randomized to Treatment Groups D, E, F, and G will stay-in house until Day 10 and return for the Day 14 assessment. Each treatment group should include equal representation of male and female subjects.

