### 4.2. Secondary Endpoints

- Area under the curve (AUC) of IFN  $\beta$ -1a and pegIFN  $\beta$ -1a from time zero to infinity (AUC0-inf)
- Maximum concentration (Cmax) of IFN  $\beta$ -1a and pegIFN  $\beta$ -1a

- $AUEC_{0-t}$  of MxA protein.
- Maximum increase from baseline in MxA protein ( $\Delta MxA_{dec, max}$ )
- Model parameter estimates for IFN  $\beta$ -1a and pegIFN  $\beta$ -1a exposure-response models (exposure parameter versus  $AUEC_{0-t}$  or  $\Delta Neopterin-C_{min}$ )

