## **6. Data Screening and Acceptance**

### **6.1. Handling of Missing and Incomplete Data**

The following imputation of missing values will be done:

- Pharmacokinetic measurements below the quantification limits will be considered equal to zero for all analyses.
- Non-pharmacokinetic measurements (e.g., neopterin, MxA) below the quantification limits will be considered equal to the lower limit of quantification for all analyses unless explicitly noted otherwise.
- Missing pharmacokinetic or pharmacodynamic data (e.g., skipped outpatient visit) will not be imputed.
- For baseline adjusted measures, samples from Day 1, time 0 will be used for calculating this derived metric. In cases where the Day 1, time 0 sample is missing or invalid, the sample collected at check-in (Day -1) will be used, followed by the screening sample. If none of these samples are available or valid, then no baseline value will be calculated for the subject.

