### **7.3. Pharmacodynamic Analysis**

#### **7.3.1 Neopterin**

Individual neopterin versus time plots will be presented for each participant. For neopterin, AUEC and maximum increase from baseline will be calculated for each participant using all on treatment timepoints. Calculations will be performed using non-compartmental analysis packages available in statistical software. The primary analysis with neopterin will use baseline-adjusted AUEC and maximum increase from baseline, while other derived measures (AUEC, pAUEC) may be calculated to evaluate how derived PD metrics impact trial design. PD parameters of IFN  $\beta$ -1a and pegIFN  $\beta$ -1a, and placebo groups will be listed and summarized using descriptive statistics (n, mean, SD, coefficient of variation, minimum, median, interquartile range, and maximum) for each treatment arm.

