## 7.5. PK/PD Analyses

The dose- and exposure-response relationship between baseline-adjusted AUEC for neopterin and  $\Delta\text{Neopterin}_{\text{dec, max}}$  and IFN  $\beta$ -1a and pegIFN  $\beta$ -1a will be explored graphically (separate assessments for both response measures). Based on these observations, model-based analyses using statistical software will be conducted separately for each drug with respect to each of the above-mentioned PD measures.

The model-based analysis will explore both dose and exposure (i.e.,  $AUC_{0-\text{inf}}$ , referred to as AUC below) as the dependent variable. Data for all dose levels for a drug, as well as placebo, will be combined for the analysis. Model selection will be based on the initial graphical assessment and will be selected from one of the following structures – linear,  $E_{\text{max}}$ , and sigmoidal. Multiple models may be evaluated based on the initial graphical analysis, in which case model selection will be based on a combination of goodness of fit plots, parameter uncertainty (i.e., parameter confidence intervals including zero), and Akaike’s information criterion (AIC). General representations for each of the model structures and parameterizations is shown below:

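### The Avonex dose- and exposure-response models pool placebo neopterin AUEC over a nominal 312 h with Avonex AUEC over 144 h; the problem is minor and avoidable

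*SAP*

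**What the plan says.** SAP 4.1 names "Neopterin area under the effect curve from time zero to last on-study timepoint" as a primary endpoint, and the SAP abbreviation table defines AUEC0-t as "area under the effect curve from time zero to last on-study sample". SAP 7.3.1 adds no fixed hour: "AUEC and maximum increase from baseline will be calculated for each participant using all on treatment timepoints".

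Follow-up differs by arm. SAP 3.1 discharges groups A, B and C on Day 7, while "Subjects randomized to Treatment Groups D, E, F, and G will stay-in house until Day 10 and return for the Day 14 assessment". The pharmacodynamic schedule in SAP Attachment A lists Days 8, 9, 10 and 14 for groups D to G only.

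SAP 7.5 models baseline-adjusted neopterin AUEC against dose and against exposure, separately for each drug: "Data for all dose levels for a drug, as well as placebo, will be combined for the analysis". Each candidate structure has one E0 and one residual error term, without random effects or covariates. SAP 4.2 makes the parameters of the "exposure-response models (exposure parameter versus" response) a secondary endpoint.

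Two rules in SAP 6.1 bear on this: "For baseline adjusted measures, samples from Day 1, time 0 will be used for calculating this derived metric", and "Missing pharmacokinetic or pharmacodynamic data (e.g., skipped outpatient visit) will not be imputed".

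The protocol handles the interval differently. Section 5.7.2.3.1 truncates AUEC once the marker has returned to baseline, and section 5.9.6.1 uses a separate interval for each dose. The SAP carries over neither rule. Protocol 5.7.1.1 marks samples after Day 7 as Plegridy only, whereas SAP Attachment A includes placebo.

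**The concern.** An AUEC grows with the time over which it is taken. In the Avonex models the zero-dose subjects are integrated over more than twice the time of the treated subjects, and the model has no term for window length. Anything in the placebo profile that is not exactly at baseline is therefore weighted differently from the same feature in an Avonex profile. It enters E0, and through E0 the estimated ED50 or EC50 (or the slope, if the linear structure is chosen). Protocol 2.2 intends the model-based work to inform dose selection for later similarity studies, so a shift in ED50 or EC50 caused only by follow-up length bears on that use.

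A missed Day 14 visit adds a second inequality. It is not imputed. If the subject is not classed as an early termination under SAP 5, that placebo AUEC would end at Day 10, so windows would also differ within placebo.

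**Working it through.** The plan states no window in hours, so there is no figure of its own to reproduce.

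**Window length.** SAP Attachment A puts 24 h on Day 2, so Day d is 24 × (d − 1) h.
- Avonex: 0, 1, 3, 6, 8, 16, 24, 32, 40, 48, 72, 96, 120, 144 h (14 samples).
- Placebo: the same, plus 168, 192, 216 and 312 h (18 samples).
- Difference 312 − 144 = 168 h; ratio 312/144 = 2.17. If Day 14 is missed, 216/144 = 1.50.
- The protocol lists 24 h under Day 1 and 48 h under Day 2. If Day d meant 24 × d h, the windows would be 168 h and 336 h, ratio 2.0.

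**Measurement noise.** Take independent error with SD σ on every sample, baseline included (assumption). Baseline-adjusted AUEC is the trapezoid sum minus window × baseline, so the baseline sample has weight 0.5 − window.
- Avonex: √(143.5² + 2,423.75) = 151.7 σ.
- Placebo: √(311.5² + 9,911.75) = 327.0 σ.
- Ratio 2.16 in SD, about 4.6 in variance. Most of it comes from multiplying one baseline sample by the window length.

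**Offset.** Suppose all arms sit a constant fraction d of baseline away from the Day 1 time-0 value after dosing. Neither the size nor the existence of d is in the documents. Placebo AUEC gains 312d and Avonex AUEC gains 144d, so the mismatch is 168d baseline-hours. With equal windows both gain 144d. That goes into E0 and leaves Emax, ED50 and slope unchanged.

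**Effect on the fit, without sampling error.** Assume a true ED50 of 15 µg. Avonex response = 144 × (d + Emax × D/(D + 15)) at 7.5, 15 and 30 µg; placebo = 312d. Fit E0 + Emax × D/(D + ED50) by least squares. At Emax 100% and d = +5%, the responses are 15.6 (placebo; 7.2 over 144 h), 55.2, 79.2 and 103.2 baseline-hours. The fit gives E0 of about 15.5 and ED50 of 19.6 µg, and 19.6/15 = 1.31.

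Fitted ED50 / true ED50:

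| Offset d | Emax 50% | 100% | 200% | 400% |
|---|---|---|---|---|
| +5% | 1.84 | 1.31 | 1.13 | 1.06 |
| +2% | 1.23 | 1.10 | 1.05 | 1.02 |
| +1% | 1.10 | 1.05 | 1.02 | 1.01 |
| −5% | 0.67 | 0.80 | 0.89 | 0.94 |
| any, equal windows | 1.00 | 1.00 | 1.00 | 1.00 |

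If exposure is proportional to dose (assumption), the EC50 ratios are the same. At +5%, fitted/true Emax is 1.07/1.01/1.00/1.00. If the linear structure is chosen instead, the slope changes by −14.8/−7.4/−3.7/−1.9%.

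**Other shapes.** A linear drift scales by (312/144)² = 4.69. A change that is over by Day 7 scales by 1.00 and causes no bias.

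**Maximum increase.** From noise alone, the expected maximum over 17 post-dose samples is 1.79 σ, against 1.67 σ over 13.

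**The case against.** The strongest reply is that baseline adjustment already deals with this. It does for a flat placebo profile, whose expected AUEC is zero over either window. A reader might infer that placebo AUEC is inflated 2.17-fold and E0 biased whatever happens. That would hold for unadjusted AUEC, which is not the modelled response. Bias needs an offset that lasts beyond Day 7, and no passage reports one. From 48 h on, the nominal samples fall at multiples of 24 h, the clock time of the baseline sample, so time-of-day variation is not an obvious source.

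Sampling error is also large. In a simulation with 12 subjects per arm, within-subject noise of 15%, and CVs of 40% for response and for exposure (all assumed), the median EC50 ratio with equal versus unequal windows was 0.97 versus 0.97 at Emax 200% and zero offset, and 0.95 versus 1.08 at +5%. The 5th to 95th percentile range with equal windows and no offset was 0.41 to 3.36. Only at Emax 50% and +5% is the shift marked: 0.97 versus 1.66. These points stand and limit the severity.

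Two replies do not remove the point. The protocol's truncation and per-dose intervals are aimed at baseline noise, but they are not in the SAP and would not give placebo and Avonex a common window. Read literally, protocol 5.7.1.1 would end placebo sampling at Day 7. However, protocol 5.1 keeps group G until Day 14 and SAP Attachment A samples it then. Protocol Table 9-1 is not in the text available for this review, so the conflict has to be reconciled rather than assumed away.

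**Conclusion.** The mismatch is real on the SAP's text: 144 h against 312 h, pooled under one E0 and one residual error term. Its certain consequence is unequal measurement noise, about 2.2-fold in SD. That matters little for EC50 unless the drug effect is small, about 50% of baseline. Bias in E0 and in ED50/EC50 (or the slope) is conditional on a sustained offset that the documents neither report nor exclude. For assumed offsets of +1% to +5% the ED50 ratio runs from 1.01 to 1.84, and the top value is the corner with the largest offset and the smallest Emax.

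A reader might take this as a flaw in the primary analysis, because the window is defined under the primary endpoints. The documents do not support that. By-arm summaries of the Avonex groups all use 144 h, the Plegridy models compare arms that all run to Day 14, and maximum increase is barely affected. Nor is Emax materially distorted. This is a minor problem, confined to the Avonex AUEC models, and worth correcting because it costs almost nothing to avoid.

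**What to change.** Add to SAP 7.5: *For the IFN β-1a models, baseline-adjusted AUEC will be computed through the Day 7 sample (nominal 144 h) for groups A, B, C and G. For the pegIFN β-1a models it will be computed through the Day 14 sample (nominal 312 h) for groups D, E, F and G.* State how a missing last sample is handled, so that every subject in a model has the same window.

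Reconcile this with the protocol's truncation rule (5.7.2.3.1) and per-dose intervals (5.9.6.1), and say which definition the models use. Reconcile protocol 5.7.1.1 with SAP Attachment A on whether placebo is sampled after Day 7, checking protocol Table 9-1.

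The cost is a few sentences and one extra derivation, placebo AUEC through Day 7, from samples the SAP already plans. No new data are needed, and maximum increase can stay as defined.

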### 4.2. Secondary Endpoints

- Area under the curve (AUC) of IFN  $\beta$ -1a and pegIFN  $\beta$ -1a from time zero to infinity (AUC0-inf)
- Maximum concentration (Cmax) of IFN  $\beta$ -1a and pegIFN  $\beta$ -1a

- $AUEC_{0-t}$  of MxA protein.
- Maximum increase from baseline in MxA protein ( $\Delta MxA_{dec, max}$ )
- Model parameter estimates for IFN  $\beta$ -1a and pegIFN  $\beta$ -1a exposure-response models (exposure parameter versus  $AUEC_{0-t}$  or  $\Delta Neopterin-C_{min}$ )

### 4.3. Exploratory Endpoints

- Additional pharmacokinetic parameters for IFN  $\beta$ -1a and pegIFN  $\beta$ -1a, including time of maximum concentration ( $T_{max}$ ), elimination rate constant ( $K_{el}$ ), area under the curve from time 0 to end of study ( $AUC_{0-t}$ ), half-life ( $t_{1/2}$ ), apparent clearance ( $CL/F$ ), and apparent volume of distribution ( $V/F$ ).
- Time course profiles, maximum increase/decrease from baseline, and AUEC for plasma proteomics and small RNA transcriptomics (set of markers be determined)

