### **5.7.1.3 Pharmacokinetic Parameters**

The following PK parameters will be determined for each subject:

- Maximum concentration (observed peak drug concentration) (Cmax)
- Time at which Cmax occurs (Tmax)
- AUC from time 0 to the sampling time corresponding to the last quantifiable concentration (Clast) (AUC0-t)
- Elimination rate constant (Kel)
- Terminal half-life (t1/2)
- AUC from time 0 extrapolated to infinity (AUC0-inf)

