### **7.4. Pharmacokinetic Analysis – IFN $\beta$ -1a and pegIFN $\beta$ -1a**

Individual serum concentration versus time plots for IFN  $\beta$ -1a and pegIFN  $\beta$ -1a will be presented for each participant.  $AUC_{0-\text{inf}}$  and  $C_{\text{max}}$  will be calculated for each participant using all on treatment timepoints as part of the secondary analysis. In addition, the following PK parameters will be calculated for each individual as exploratory analyses:  $AUC_{0-t}$ ,  $T_{\text{max}}$ , apparent clearance (CL/F), apparent volume of distribution (V/F), elimination rate (Kel), and terminal half-life ( $t_{1/2}$ ). PK

parameters will be calculated for each participant using all on treatment timepoints. All parameters will be summarized using descriptive statistics (n, geometric mean, coefficient of variation, minimum, median, interquartile range, and maximum) for each IFN  $\beta$ -1a and pegIFN  $\beta$ -1a treatment arm.

Calculations will be performed using non-compartmental analysis packages available in a statistical software. Serum concentrations below the limits of quantification will be set to zero for the purpose of this analysis. Subjects with all samples below the limit of quantification will be excluded from PK summaries.  $AUC_{0-\text{inf}}$ ,  $t_{1/2}$ , and  $K_{el}$  for subjects will only be included for subjects with 3 or more concentration values on the terminal portion of the pharmacokinetic curve and with an adjusted coefficient of determinations ( $R^2$ ) greater than 0.80.

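### SAP 7.4 screens AUC0-inf, t1/2 and Kel on terminal fit but not the exploratory CL/F and V/F computed from them, and AUC0-t is defined differently in protocol and SAP

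*SAP*

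**What the plan says.** **Terminal-fit rule.** SAP 7.4 lists the exploratory parameters to be calculated for each individual, among them "apparent clearance (CL/F), apparent volume of distribution (V/F"). It adds that "parameters will be calculated for each participant using all on treatment timepoints" and that all parameters are summarised by arm. The acceptance rule comes at the end of the section and is confined to Kel, AUC0-inf and t1/2. It says that these values "for subjects will only be included for subjects with 3 or more concentration values on the terminal portion of the pharmacokinetic curve", and it also requires adjusted R2 above 0.80. CL/F and V/F are not in that sentence, and no other rule covers them.

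**AUC0-t.** Protocol 5.7.1.3 (and the synopsis) defines it as "AUC from time 0 to the sampling time corresponding to the last quantifiable concentration". The SAP abbreviation table has "area under the concentration-time curve from time zero to last on-study sample", and SAP 4.3 has "area under the curve from time 0 to end of study". SAP 6.1 adds: "Pharmacokinetic measurements below the quantification limits will be considered equal to zero for all analyses". SAP 7.4 repeats this for the non-compartmental analysis: "Serum concentrations below the limits of quantification will be set to zero for the purpose of this analysis".

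**Status.** AUC0-t, Kel, t1/2, CL/F and V/F are exploratory in SAP 4.3. AUC0-inf and Cmax are secondary in SAP 4.2, and the exposure-response models in SAP 7.5 use AUC0-inf. The protocol's parameter list does not include CL/F or V/F.

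**The concern.** A subject's AUC0-inf and Kel can be rejected as unreliable while two quantities calculated from those same numbers are still summarised. The parameters in one table would then rest on different subjects. The extra subjects in CL/F and V/F would be those with the poorest terminal data, who tend to be those with the lowest exposure. The study is meant to supply values and variability of PK parameters at three doses for planning later trials, so an unannounced change of denominator is unhelpful even in exploratory rows.

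The AUC0-t issue is separate. One parameter has two definitions, and they give different numbers whenever a subject has unquantifiable samples after the last measurable one. A report that says only AUC0-t would leave the reader unable to tell which was used.

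**Working it through.** The plan states no figure on this point, so there is none to reproduce.

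**1. Dependence of CL/F and V/F on the screened quantities.** In standard non-compartmental analysis:
- AUC0-inf = AUC to the last quantifiable value + Clast / Kel
- CL/F = dose / AUC0-inf
- V/F = (CL/F) / Kel = dose / (AUC0-inf × Kel)

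If Kel is too shallow, the extrapolated area is too large. CL/F is then too low, and V/F is divided by too small a Kel.

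**2. Assumptions (none is in the documents).** One compartment with first-order absorption; half-life 10 or 20 h; ka 0.15/h; log-SD 0.385 on exposure (40% CV) and 0.2 on the elimination rate; 15% assay error; 3,000 subjects per scenario. LLOQ is 50, 25, 12.5 or 6.25% of typical Cmax. Sampling follows SAP Attachment A to Day 7 (144 h), and the terminal slope is the best adjusted-R2 fit on at least three points. Two half-lives by four LLOQs gives 8 scenarios.

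The doses run 1:2:4 for each drug. If exposure is dose-proportional, an LLOQ at 12.5% of high-dose Cmax is 25% at the intermediate dose and 50% at the low dose.

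**3. Who is affected (half-life 10 h).**
- LLOQ 50% of Cmax: 79% fail the rule, but only 11% of all subjects fail and still have a slope. Passing subjects are 100 − 79 = 21%, so the extra ones form 11 / (21 + 11) = 34% of the CL/F and V/F set. In an arm of 12 that is 12 × 0.11 = 1.3 subjects beside 12 × 0.21 = 2.5 who pass.
- LLOQ 25%: 36% fail and 12.5% fail with a slope. The extra share is 12.5 / (64 + 12.5) = 16%, or 12 × 0.125 = 1.5 subjects beside 12 × 0.64 = 7.7.

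**4. Effect of keeping them.** Each estimate was divided by that subject's own simulated true value, and geometric means were compared with and without the rejected fits:
- LLOQ 25-50% of Cmax: V/F up about 4-8%, CL/F down about 3-11%.
- LLOQ 12.5% and below: about 1% or less for both.

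This isolates estimation error. The printed geometric means also depend on who is removed. Rejected subjects tend to have low exposure and hence high true CL/F and V/F. The printed V/F mean therefore moves more (roughly 8-14% at LLOQ 25-50%), while for CL/F the two influences oppose each other and the printed mean can move either way.

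**5. AUC0-t.** With trailing values set to zero and the linear trapezoid, the SAP version adds Clast × (gap to next sample) / 2. For a 24 h gap that is 12 h × Clast; for Day 10 to Day 14 (216 to 312 h, a 96 h gap) it is 48 h × Clast. SAP over protocol, with each version as a fraction of true AUC over 0-144 h:
- LLOQ 50%: 18-24% higher.
- LLOQ 25%: about 8-11% higher (0.85 / 0.79 = 1.08; 0.84 / 0.76 = 1.11). SAP is 0.84-0.85 of truth, protocol 0.76-0.79.
- LLOQ 12.5%: 6-7% higher. SAP 0.94-0.95, protocol 0.88-0.89.
- LLOQ 6.25%: 3-5% higher. SAP 0.98, protocol 0.94-0.95.

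The SAP version was closer to truth in all 8 scenarios.

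A wider set of 24 scenarios covered both drugs' sampling times (half-lives 10-30 h and 30-78 h, LLOQ 2-20% of high-dose Cmax). The group geometric mean was higher under the SAP by 2.3-30.6% at the low dose, 0.9-16.4% at the intermediate dose and 0.3-8.9% at the high dose.

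**The case against.** **The rule may be meant to carry over.** CL/F and V/F derive from AUC0-inf and Kel, so an analyst may drop them with their parents. That is a sensible reading, but the SAP does not say it. The text names three parameters and says the rest are calculated for each participant.

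**Not every rejected subject stays in.** A reader might infer that all subjects failing the rule remain in CL/F and V/F. Many have fewer than three post-peak values, hence no slope and no CL/F or V/F at all. Only those with a fitted but rejected slope matter, which is why the effect is modest. This stands.

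**The SAP's AUC0-t may be the better one.** A reader might infer that the protocol definition is right and the SAP's is an error. The check does not support that: on the Avonex-type sampling times the added triangle partly recovers a real tail. No such comparison with true AUC was made on the Plegridy times.

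**Software may settle it.** The SAP leaves the calculation to non-compartmental packages, and many stop at the last positive value by default. The AUC0-t discrepancy would then produce no numerical change. This too stands, but it means that the result depends on an option the SAP does not state.

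**Low doses.** The group-mean difference in AUC0-t was largest at the low dose in all 24 wider scenarios. For a single typical subject it was largest there in only 17, tied in 3 and smaller than at another dose in 4. With 12 per arm the order need not hold.

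**Conclusion.** The point holds as a minor gap among exploratory parameters. As written, the SAP summarises CL/F and V/F for some subjects whose AUC0-inf and Kel it has rejected. The resulting estimation error is about +4-8% in V/F and −3-11% in CL/F at LLOQ 25-50% of typical Cmax, and about 1% or less at 12.5% and below. These sizes rest wholly on assumed kinetics and LLOQ. The CL/F and V/F figures are for the Avonex sampling times and should not be read across to Plegridy.

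The AUC0-t definitions do conflict, by about 3-24% on the Avonex times depending on LLOQ. The documents support reconciling them, not preferring one.

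A reader might infer that the PK results in general are distorted. They are not: trailing zeros and the scope of the terminal-fit rule leave Cmax, AUC0-inf and the AUC0-inf exposure-response models unchanged under standard non-compartmental analysis.

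**What to change.** 1. In SAP 7.4, extend the subject of the terminal-fit sentence to AUC0-inf, t1/2, Kel, CL/F and V/F.
2. Report n for every PK parameter at every dose, so that the loss from the rule is visible.
3. Give AUC0-t one definition in the protocol, the SAP abbreviation table and SAP 4.3. State how unquantifiable values after the last measurable one enter the integral, and set the software option to match.

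The cost is a few wording changes and none to conduct. The downside is fewer subjects for CL/F and V/F, and a selected group: if many low-dose subjects fail, the summaries describe those with higher exposure. The reported n should be read with that in mind. If the protocol's AUC0-t is chosen, more of the true tail may be left out; if the SAP's is chosen, the value depends on the sampling gap after the last measurable sample. Either is workable once stated.
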